## 157 Covariates

- We will collect the following covariates ascertained on or before ULT initiation to build the inverseprobability of censoring weighting as detailed above:
- demographics: age, sex (male or female), latest body mass index (BMI) available only in CPRD,
   socioeconomic deprivation assessed using the index of multiple deprivation (IMD) at patient
- socioeconomic deprivation assessed using the index of multiple deprivation (IMD) at patient
   level in CPRD and income and educational level in VEGA, latest smoking status (current, past, or
- non-smoker) available only in CPRD, latest alcohol intake (current, past, or no intake) available
   only in CPRD. Demographic variables will be ascertained within the 5 years before ULT initiation,
- 165 gout-related variables: gout duration (years), presence of subcutaneous tophi, number of anti-
- 166 inflammatory prescriptions (colchicine, NSAIDs, and corticosteroids) in 12 months before ULT
- 167 initiation, number of consultations in primary care for gout and number of hospitalisations for

- gout in the 12 months before ULT initiation, ULT molecule (i.e., febuxostat, allopurinol,
   uricosurics) and dose (high vs low starting dose), co-prescription of gout flare prophylaxis with
   colchicine and/or non-steroidal anti-inflammatory drugs on the date of ULT initiation (i.e.,
   prescription length ≥21 days);
- 172 general health and other cardiovascular comorbidities: Charlson Comorbidity Index [28], 173 cardiovascular comorbidities not included in the Charlson Comorbidity index (i.e., hypertension, 174 atrial fibrillation, and hypercholesterolemia), heart failure, diabetes with and without target 175 organ damage, chronic kidney disease (stage 3,4,5), dementia, peripheral vascular disease, 176 COPD, cancer, HIV/AIDS European Society of Cardiology cardiovascular risk (high/very high vs 177 moderate/low), history of cardiovascular events before ULT initiation, number of consultations 178 in primary care for any reason and number of hospitalisations for any cause in the 12 months 179 before ULT initiation,
- 180 medications (low-dose acetylsalicylic acid (ASA), non-ASA antiplatelet agents, statins, fibrates,
- other lipid-lowering agents, potassium-sparing diuretics, thiazides, loop diuretics, beta-blockers,
   calcium-channel blockers, angiotensin-converting enzyme inhibitors and angiotensin receptor
- 183 blockers, other anti-hypertensive agents, nitrates, and oral anticoagulants. Prescriptions will be
- 184 categorised as current (last prescription within 60 days before ULT initiation in CPRD and last
- 185 prescription within 120 days before ULT initiation in VEGA) or past/no prescription. The duration
- 186 was selected based on clinical input as the mean length of prescriptions in the UK and in Sweden
   187 differs.

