## 77 Study setting and data source

78 This study will be carried out in England and Sweden using data recorded in the course of routine

- 79 clinical care for people with gout managed in primary care. General Practices contributing to the
- 80 Clinical Practice Research Datalink (CPRD) Aurum and the Western Sweden Regional Healthcare
- 81 Database (VEGA) will be included in the study.
- 82 We will extract CPRD data for the period between 01/01/2007 and 29/03/2021 and VEGA data for
- 83 the period between 01/01/2007 and 31/12/2017 covering the periods over which linkage with

secondary-care data will be available. Indeed, the first recommendations for the management of
gout by the BSR and the EULAR were published in 2007 and 2006, respectively [15,16].

86 • Clinical Practice Research Datalink Aurum

CPRD database includes information from more than 38 million individuals, representative of the English population in terms of age, sex, and ethnicity [17]. CPRD data include information on demographic characteristics, lifestyle factors, diagnoses, primary care prescriptions, laboratory results, and immunisations [17]. Primary care data are linked to patient-level index of multiple deprivation (IMD) scores, hospitalization records via linkage with the Hospital Episode Statistics (HES) dataset, and information on date and causes of death via linkage with the Office for National Statistics (ONS) dataset.

Western Swedish Health Care Register

VEGA contains information about all healthcare contacts for both primary and secondary healthcare
 in western Sweden (~1.7 million inhabitants). All diagnoses given by physicians are registered
 according to the Swedish version of the International Classification of Disease (ICD) 10 codes.

98

94

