## 99 Eligibility criteria

- 100 The study population will consist of English and/or Swedish patients for whom research-quality data
- 101 are available, who are aged ≥18 years at first gout diagnosis in either primary care or secondary care
- 102 (whichever came first), are newly diagnosed with gout (defined as a new diagnostic code for gout
- 103 or gout flare at least 12 months after registration at their current general practice, and no prior
- 104 codes indicating history of gout to ensure only incident cases are included [18]) within the study 105 period, receive their first ULT prescription on or after the day of new gout diagnosis and have a
- 106 serum urate level >360 micromol/l before ULT initiation.
- Previous research has found a positive predictive value of gout diagnosis in electronic health records
  to be acceptable when compared to classification criteria for gout [19–21].
- 109

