## 110 Treatment strategies

- 111 Intervention arm (T2T-ULT arm): To emulate ULT initiation aiming to achieve the serum urate target
- 112 of  $\leq$  360 micromol/l within 12 months after ULT initiation, serum urate target will be ascertained by
- 113 the earliest recorded serum urate measurement  $\leq$ 360 micromol/l within 12 months after ULT 114 initiation.
- 115 *Comparison arm (FAF-ULT arm):* Emulation of ULT initiation without an aim to achieve a serum urate
- 116 target will use patients without any recorded serum urate measurements or with serum urate >360
- 117 micromol/l within 12 months after ULT initiation.
- 118 Previous randomised controlled trials showed that the serum urate target can be achieved within 6
- 119 months from the first ULT prescription [1,22,23]. However, the proportion of patients achieving the
- 120 serum urate target in clinical practice is expected to be lower [2]. Therefore, we will allow 12 months
- 121 of grace after ULT initiation for participants to achieve the serum urate target.
- 122

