### 148 Follow up

- 149 People will be followed up from the first ULT prescription to the earliest date of a cardiovascular
- event, transfer out of the primary-care practice, death, 5 years from the first ULT prescription, studyend, and last consultation in primary care.
- Artificial censoring will be applied as follows: 1) clones assigned to the T2T-ULT arm will be censored at 12 months from ULT initiation if they do not achieve the serum urate target, 2) clones assigned to the FAF-ULT arm will be censored at the time they achieve the serum urate target within 12
- 154 to the FAF-OLT and will be censored at the time they achieve the seruin drate target v
- 155 months after the first ULT prescription.
- 156

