## 202 Inverse probability of censoring weighing

- In this study, we will estimate the inverse probability of censoring weights by fitting a pooled logistic
   model for the monthly probability of remaining uncensored, including variables for time (in its linear
- and/or quadratic terms depending on the data structure) and the baseline covariates. To avoid
  undue influence of outliers, weights will be truncated at the 99.5th percentile in case of extreme
  weights.
- 208 The inverse probability of censoring weighting will be built using two different models including a
- 209 different set of covariates as shown in the following table.

Variables	Model 1	Model
Age	Y	Y
Sex (male vs female)	Y	Y
Body Mass Index	N	Y
Socioeconomic deprivation	Y	Y
Smoking status	N	Y
Alcohol intake	N	Y
Gout duration (years)	Y	Y
Subcutaneous tophi (y/n)	Y	Y
Number of anti-inflammatory prescriptions (colchicine, NSAIDs, and corticosteroids) in	Y	Y
12 months before ULT initiation		
Number of consultations in primary care for gout and number of hospitalisations for	Y	Y
gout in the 12 months before ULT initiation		
ULT molecule (i.e., febuxostat, allopurinol, uricosurics)	Y	Y
ULT dose (high vs low starting dose)	Y	Y
Co-prescription of gout flare prophylaxis with colchicine and/or non-steroidal anti-	Y	Y
inflammatory drugs on the date of ULT initiation (i.e., prescription length ≥21 days)		
Charlson comorbidity index	N	Y
Cardiovascular comorbidities not included in the Charlson Comorbidity index (i.e.,	Y	Y
hypertension, atrial fibrillation, and hypercholesterolemia)		
Acute or chronic ischaemic heart disease, heart failure, diabetes with and without	Y	Y
target organ damage, chronic kidney disease (stage 3,4,5), dementia, peripheral		
vascular disease, COPD, cancer, HIV/AIDS		
History of cardiovascular events before ULT initiation	Y	Y
European Society of Cardiology cardiovascular risk	Y	Y
Number of consultations in primary care for any reason and number of hospitalisations	Y	Y
for any cause in the 12 months before ULT initiation		
Proportion of days covered by ULT between the date of ULT initiation and the end of	Y	Y
the grace period		N N
Low-dose ASA	Y	Y
Non-ASA antiplatelet agents	Y	Y
Statins	Y	Y
Fibrates	Y	Y
Other lipid-lowering agents	Y Y	Y
Potassium-sparing diuretics	Y Y	Y
Thiazides		Y
Loop diuretics	Y	Y
Beta-blockers	Y Y	Y
Calcium-channel blockers	Y Y	Y
Angiotensin-converting enzyme inhibitors	Y Y	Y
Angiotensin receptor blockers		Y
Other anti-hypertensive agents	Y	Y
Nitrates	Y	Y

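### Neither weight model includes pre-treatment serum urate, although urate reaching 360 micromol/l decides the artificial censoring in both arms

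*Protocol*

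**What the plan says.** Protocol, Eligibility criteria: each patient must have a "serum urate level >360 micromol/l before ULT initiation". The value therefore exists for everyone in both databases, but it serves only as an entry threshold.

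Protocol, Treatment strategies and Follow up: the T2T arm is defined by "the earliest recorded serum urate measurement" at or below 360 micromol/l within 12 months. Clones in the fire-and-forget (FAF) arm "will be censored at the time they achieve the serum urate target within 12" months. T2T clones who have not reached target are censored at month 12.

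Protocol, Covariates: "We will collect the following covariates ascertained on or before ULT initiation", followed by a list. Its gout items are "gout-related variables: gout duration (years), presence of subcutaneous tophi", then anti-inflammatory prescriptions, gout consultations and admissions, drug, starting dose and flare prophylaxis.

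Protocol, Inverse probability of censoring weighing: a pooled logistic "model for the monthly probability of remaining uncensored, including variables for time (in its linear" and/or quadratic form), with a yes/no entry for each covariate in Models 1 and 2. Both models also contain "Proportion of days covered by ULT between the date of ULT initiation and the end of" the grace period.

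Protocol, Study setting and data source: "CPRD data for the period between 01/01/2007 and 29/03/2021 and VEGA data for" 2007 to the end of 2017.

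**The concern.** Cloning makes the arms identical at time zero, in urate as in everything else. Censoring on urate then undoes that balance. A patient who starts just above 360 micromol/l has less far to fall than one who starts well above it, so clones left in the T2T arm after month 12 will tend to have had lower starting urate than clones left in the FAF arm. The Statistical analysis section itself says that artificial censoring is usually informative and relies on the weights to repair it. Weights can do so only for variables they contain or that their variables stand in for.

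If starting urate also carries cardiovascular risk not captured by the other covariates, the remaining imbalance favours T2T, which is the direction of the superiority hypothesis. Calendar year of initiation is missing too, which is a lesser point.

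**Working it through.** **Is it really absent?** I compared the covariate list with every row of the weight table. Neither contains pre-treatment urate, or a date or year of ULT initiation. The label of the last table row is not legible in the available text; by the order of the list it is oral anticoagulants. The only time term belongs to the monthly model, so it is follow-up time, not calendar time. Model 2 adds BMI, smoking, alcohol and the Charlson index, so comparing it with Model 1 cannot expose confounding by urate. No sensitivity or stratified analysis uses starting urate or calendar period. The protocol fixes the set variable by variable, so this is not a detail left for a later document.

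**How large could it be?** The protocol gives no figure for residual confounding, so there is none to reproduce.

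Inputs from the protocol (Feasibility count and sample size considerations):
- 28% reach target within a year
- MACE rate 17 per 1,000 person-years
- planned difference 1 per 1,000 person-years
- 5 years of follow-up (Outcomes)

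Assumptions, not in the documents:
- Starting urate *z* is standard normal.
- The odds ratio (OR) for reaching target is 0.5 to 0.7 per SD.
- The MACE hazard ratio (HR), beyond the listed covariates, is 1.00 to 1.15 per SD.
- Attainment is spread evenly over the 12 months.
- The true treatment effect is null, and the weights do nothing for urate.

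Model: logit p(z) = a + ln(OR)·z, with a set so that mean p = 0.28, and h(z) = 17 × HR^z / E[HR^z]. Write E for the average over z. Depletion by events is included in the results.

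1. *Year 1.* The T2T arm is still the whole cohort, at about 17 per 1,000. The FAF arm loses attainers gradually: at time t its rate is E[(1 − p·t)·h] / E[1 − p·t].
2. *Years 2 to 5.* T2T holds attainers only, with rate E[p·h]/0.28. FAF holds non-attainers only, with rate E[(1 − p)·h]/0.72.
3. *Five-year average difference* = (year 1 + 4 × years 2–5) / 5.

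| OR per SD | HR per SD | Attainers start lower by (SD) | Year 1 | Years 2–5 | 5-year average |
|---|---|---|---|---|---|
| 0.5 to 0.7 | 1.00 | 0.35 to 0.63 | 0 | 0 | 0 |
| 0.7 | 1.05 | 0.35 | 0.04 | 0.29 | (0.04 + 1.16)/5 = 0.24 |
| 0.5 | 1.05 | 0.63 | 0.07 | 0.52 | (0.07 + 2.08)/5 = 0.43 |
| 0.6 | 1.15 | 0.49 | 0.14 | 1.14 | (0.14 + 4.56)/5 = 0.94 |
| 0.5 | 1.15 | 0.63 | 0.18 | 1.48 | (0.18 + 5.92)/5 = 1.22 |

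The last four columns give the spurious T2T advantage; rates are per 1,000 person-years.

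Hand check of years 2–5: the difference is roughly 17 × ln(HR) × SD gap. For OR 0.5 and HR 1.15 this is 17 × 0.140 × 0.63 = 1.5. For OR 0.7 and HR 1.05 it is 17 × 0.0488 × 0.35 = 0.29.

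**On the plan's own scale, 5-year survival.** The planned difference is exp(−5 × 0.016) − exp(−5 × 0.017) = 0.9231 − 0.9185 = 0.0046, or 0.46 percentage points. The largest bias above is about 5 × 0.00122 × 0.92 = 0.0056, or 0.56 points.

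**The case against.** The best defence is that much of what links urate to MACE is already modelled. Both models hold chronic kidney disease stage, thiazide, loop and potassium-sparing diuretics, diabetes, hypertension, tophi and the European cardiovascular risk category. Adherence, drug and starting dose are there as well. Only an association of urate with MACE beyond all of these causes bias, and no part of the protocol gives one. This stands, and it is why the range must start at zero. It does not remove the point, because a measured value held for every patient is being replaced by indirect stand-ins.

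A reader might infer that the strongest predictor of reaching target has been left uncontrolled. The documents do not support that. They rank no predictors. Attainment also requires a test, since untested patients count as FAF, and it depends on adherence and dose. Urate is not directly controlled, which is a weaker statement.

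A reader might also compare attainers with non-attainers from time zero and report 0.3 to 1.5 per 1,000 person-years. That ignores cloning, under which the T2T arm remains the whole cohort for the first year, and it leaves out the case of no residual association.

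The planned negative control outcomes may signal residual confounding. They cannot correct it or identify urate as its source.

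Finally, if urate predicts censoring strongly and MACE only weakly, adding it mainly inflates the weights. That cost is real but has not been quantified.

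**Conclusion.** The omission is certain; its effect on the result is conditional. Both models leave out a direct determinant of reaching 360 micromol/l that every eligible patient has on record, in a design where that event decides the censoring. Under the stated assumptions the spurious T2T benefit is 0 to about 1.2 per 1,000 person-years. It is zero if urate adds nothing to MACE risk beyond the listed covariates, and at the upper end it exceeds the planned difference of 1. The odds and hazard ratios are assumptions, so this range shows what is possible and is not an estimate.

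Calendar year is secondary. Initiation spans 2007 to 2021 in CPRD and 2007 to 2017 in VEGA, and practice may have shifted, but the documents give no trend in attainment or MACE and I attach no size to it.

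The change should be made because it is cheap and the possible bias runs towards the hypothesis.

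**What to change.** Add the latest serum urate before ULT initiation to Models 1 and 2 in both databases, as a continuous variable with a spline or quadratic term. As a secondary change, add calendar year of ULT initiation to both models. If either is left out, give the reason in the protocol.

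The eligibility rule sets no look-back window and does not say that the qualifying value is the latest one. State which value enters the model, and report how long before initiation it was taken, since some values may be old.

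Cost: no new data collection, because eligibility guarantees a urate value and prescription dates are already held. The weights will be somewhat more variable; truncation at the 99.5th percentile is already planned. Reporting the weight distribution, and the balance of starting urate between the weighted arms after month 12, would show whether the repair worked.

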### 188 Statistical analysis

- 189 All descriptive statistics will be reported as number (percentage), mean (standard deviation (SD), or
- 190 median (interquartile range (IQR)) as appropriate.
- 191 Although cloning allows us to account for observed confounding at baseline, the artificial censoring 192 introduced is usually informative [12]. The proposed approach to address this problem is to use 193 inverse probability of censoring weighting. The purpose of the weights is to up-weight patients 194 remaining adherent to the protocol so that they represent censored patients, and as such, maintain 195 the comparability of the study arms throughout the grace period. Survival curves will be estimated 196 using a non-parametric Kaplan-Meier estimator weighted for the inverse probability of censoring 197 weights. The 95% confidence intervals for the difference in 5-year survival and the difference in 198 restricted mean survival times will be obtained using a non-parametric bootstrap with 1000 199 replicates [29].
- 200 First, data from Sweden and the UK will be analysed separately. Then, results will be meta-analysed.
- 201 All analyses will be performed using Stata, version 18 (StataCorp, Texas, USA).

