## 64 Study design

65 This study will emulate an investigator-initiated, pragmatic, multicentre, two-arm, open-label, 66 randomised, superiority treatment strategy trial in gout patients initiating ULT for the first time using 67 a cloning, censoring, and weighting approach [11]. Cloning is used to assign people to treatment 68 duration strategies at time zero (i.e., at ULT initiation), eliminating immortal time bias and creating 69 two identical study arms at baseline. Then, a clone is censored when their available data (i.e., the 70 serum urate levels) are no longer compatible with the treatment strategy of the arm they entered, 71 but the follow-up continues for that individual in the arm of the compatible strategy. This induces 72 informative censoring [12], which will be addressed using inverse probability weighting [13].

- The emulation of target trials using real-world data can lead to high-quality evidence and high concordance with randomised controlled trials when closer emulation of trial design and measurements is adopted [14].
- 76

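### The planned weights target artificial censoring in the grace year; practice transfer and last consultation over the 5 years are left unweighted, which biases the 5-year contrast if loss differs by arm and by cardiovascular risk

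*Protocol*

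**What the plan says.** The Follow up section has two kinds of censoring. Observation ends at the earliest of a cardiovascular event, "transfer out of the primary-care practice, death, 5 years from the first ULT prescription, studyend, and last consultation in primary care". Separately, artificial censoring enforces the strategies: "clones assigned to the T2T-ULT arm will be censored at 12 months from ULT initiation" if the urate target has not been met, and FAF clones are censored when they reach it within those 12 months.

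The Study design section says that censoring clones for incompatibility with their arm induces "informative censoring [12], which will be addressed using inverse probability weighting [13]". The Statistical analysis section repeats that the artificial censoring is usually informative and offers weighting as the remedy. It states the purpose of the weights as up-weighting patients "remaining adherent to the protocol so that they represent censored patients, and as such, maintain" "the comparability of the study arms throughout the grace period". The Kaplan-Meier estimator carries these weights and no others.

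The section on inverse probability of censoring weighting fits a pooled logistic "model for the monthly probability of remaining uncensored, including variables for time" and baseline covariates. It does not say which censoring events count. The primary outcome runs to 5 years.

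**The concern.** The grace period covers one year of the five. In the other four, a patient who transfers out or stops consulting is removed, and a Kaplan-Meier estimator without a weight for that removal treats those who remain in the arm as representing those who left.

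There is reason to doubt this. After month 12 everyone still in the T2T arm has a recorded urate at or below target, so each had some contact with care. The FAF arm includes patients with no urate test at all. Contact with primary care therefore helps to define the arms, and the date of last consultation also ends follow-up. If leavers differ from stayers in cardiovascular risk, and do so to a different extent in the two arms, both planned contrasts (5-year survival difference and restricted mean difference) are biased. The effect sought is small, so a modest bias could matter.

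**Working it through.** **Plan's own figures.** The protocol states no loss rate, so there is none to reproduce. The sample size section gives a MACE rate of 17/1,000 person-years in the unexposed and a difference of 1/1,000 person-years. Over 5 years:

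(1 − e^(−0.085)) − (1 − e^(−0.080)) = 0.0815 − 0.0769 = 0.0046, or 4.6 per 1,000.

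The power claimed for that difference is a separate matter and is not used here.

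**Assumed inputs (not in the protocol).**
- No true effect; average hazard 17/1,000 person-years in both arms.
- 20% of patients are at high risk, with hazard 34 or 55/1,000. The other 80% then have (17 − 0.2 × 34)/0.8 = 12.75, or (17 − 0.2 × 55)/0.8 = 7.5 per 1,000.
- T2T annual loss: 6% high-risk, 4% other, as constant rates.
- Clones of one person share loss until artificial censoring separates them. Both arms therefore use the T2T loss rates in year 1, and rates differ only from month 12.

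**Formula.** For risk class i with share w, hazard h and cumulative loss C, the proportion still observed is S_i(t) = w_i·exp(−h_i·t − C_i(t)). With loss treated as independent, the Kaplan-Meier risk tends to 1 − exp(−∫ h̄(t) dt) over 0 to 5 years, where h̄(t) = ΣS_i·h_i / ΣS_i.

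**Results: FAF minus T2T 5-year risk per 1,000, true value 0.**

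| FAF annual loss from month 12 (high-risk / other) | High-risk hazard 34 | High-risk hazard 55 |
|---|---|---|
| 6% / 4% (same as T2T) | 0 | 0 |
| 9% / 6% (50% faster in both classes) | −0.2 | −0.5 |
| 12% / 5% | −1.1 | −2.3 |
| 20% / 5% | −2.6 | −5.6 |

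For the smallest value in the third row, the apparent risks are 78.85 (FAF) and 79.94 (T2T). For the largest value in the table they are 70.41 and 75.97.

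Against 4.6 per 1,000, the second row is about 5 to 10% of the effect sought. The third and fourth rows together span about 24 to 121%. Assuming no loss at all in year 1 gives the same results to within 0.1 per 1,000.

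**What drives the size.** Five-year loss in T2T is 1 − 0.8·e^(−0.20) − 0.2·e^(−0.30) = 19.7%. In FAF it is 1 − 0.8·e^(−0.28) − 0.2·e^(−0.42) = 26.4% in the second row and 1 − 0.8·e^(−0.24) − 0.2·e^(−0.54) = 25.4% in the third. Total loss is nearly the same, but the bias is about five times larger in the third row. What matters is whether high-risk patients in particular leave one arm faster.

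**Equal loss with a real effect.** With 20% lost in each arm and a true 5-year difference of 0.43 to 0.45 percentage points, the bias is at most about 0.02 points, even when high-risk patients leave at 2 to 3 times the rate of others.

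**The case against.** The strongest reply is that the operative specification models remaining uncensored, month by month, without restricting this to artificial censoring or to the first year. It could be meant to include loss, and finer detail may sit in an analysis plan that is not shown. The ambiguity is real. But the Study design and Statistical analysis sections both tie the weights to artificial censoring, and the latter ties their purpose to the grace period. The protocol itself also fixes the covariates, the truncation and the estimator. If loss was meant to be covered, the text should say so.

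Second, the weights use prior consultations, admissions, comorbidity and deprivation, so measured frailty and healthcare use should be balanced at month 12. That stands, and it weakens the simple picture of engaged T2T patients against disengaged FAF patients. It does not make later loss independent of risk within an arm, or alike between arms.

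Third, one planned sensitivity analysis drops FAF patients without a urate measurement, and negative control outcomes are planned. Both may reveal part of the problem. Neither corrects for loss.

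A reader might infer that this loss could produce a false benefit, or that the bias could approach twice the effect sought. The documents support neither inference. Every scenario tabulated above hides a benefit. A spurious benefit needs the opposite pattern: for example, 30% lost in T2T against 10% in FAF, with high-risk patients leaving 2 to 3 times as fast, gives 0.19 to 0.43 points. Nothing in the protocol points to that pattern. Values of 1.7 to 8.6 per 1,000 (37 to 187% of 4.6) arise only if arm-specific loss starts at time zero, when clones of the same person largely share their loss.

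**Conclusion.** The point holds as a conditional weakness that is cheap to repair. As written, transfer out and last consultation are treated as independent censoring over a 5-year horizon, while the stated purpose of the weights stops at 12 months. Bias in the survival and restricted mean differences requires loss that differs by arm and is related to cardiovascular risk; its direction follows the loss pattern and cannot be told from the protocol.

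Under assumed rates, the size runs from 0.2 to 0.5 per 1,000 (mild pattern) to 1.1 to 5.6 per 1,000 (selective loss of high-risk FAF patients), against the 4.6 per 1,000 sought. The upper end rests on a hazard ratio of about 7 between risk classes (55/7.5) and on a strong interaction of arm with risk in loss. The protocol gives no evidence for either. The restricted mean difference was not computed separately.

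**What to change.** In the Statistical analysis section and the section on inverse probability of censoring weighting:

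- State that the existing pooled logistic model covers artificial censoring.
- Add a separate, arm-specific pooled logistic model for monthly loss to follow-up (transfer out, last consultation) over the full 5 years. Use the baseline covariates already listed and, where available, consultations and admissions updated over time.
- Multiply its inverse-probability weight into the artificial-censoring weight before the Kaplan-Meier step, and refit it in each bootstrap replicate.
- Report loss by arm, preferably also by baseline cardiovascular risk, since the total alone does not show how selective the loss is.

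The cost is one more model on data already held and slightly wider intervals. The weight reduces bias only as far as measured covariates explain loss, so the loss table is needed alongside it.
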